4.2.2 Study description and design rationale

The objective of this study is to assess the usability of SYDNEY in high or very high cardiovascular risk patients with hypercholesterolemia not adequately controlled with their lipid-modifying therapy (LMT).

Study population should include patients with either heterozygous familial hypercholesterolemia (heFH) or non-FH patients at high or very high cardiovascular risk (including patients with coronary heart disease [CHD], non-CHD CVD, and other risk factors), not adequately controlled with a stable daily dose of atorvastatin (20 mg or 40 mg), or rosuvastatin (10 mg or 20 mg) for at least 4 weeks prior to the screening visit, with or without LMT.

This is a randomized, open-label, 16-week study, after a screening period of up to 2 weeks:

Treatment periods include:

- A parallel-arms period with one of the 2 devices (SYDNEY or AI) for the first 4 weeks.
Patients will be randomized to receive alirocumab 300 mg Q4W, self-administered using either SYDNEY or AI on Week 0 (Day 1) for the first injection, that will be done on site, under supervision and guidance of the Investigator or designee.
- A single-arm period (with SYDNEY only) for the subsequent weeks until Week 16
All patients will receive alirocumab 300 mg Q4W, self-administered using only SYDNEY, for the 2nd, 3rd and 4th injections on Week 4, Week 8 and Week 12 respectively.
The Week 4 and Week 8 injections will be performed at home or on-site without supervision or guidance. The Week 12 injection will be performed at the site and will be under observation only; there will be no guidance provided. Therefore the Week 12 injection is also considered to be unsupervised.

Patients assigned to the AI will switch to SYDNEY after the first self-injection to allow for the maximum use of SYDNEY in this study (ie, a total of 180 unsupervised injections to be performed with the new device), for the evaluation of safety, efficacy and ease of use of the 2 mL device in all the study participants.

The proposed design would support bridging the data for the alirocumab 300 mg monthly dosing regimen obtained with the currently marketed 1 mL AI to the new 2 mL SYDNEY.

It also allows for a descriptive comparison of the two devices up to Week 4 only (after the first dose) for pharmacokinetic/pharmacodynamic (PK/PD) and safety (including local injection site reactions [LISR]).

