10.3.4 Handling of patients after permanent treatment discontinuation

Patients will be followed-up according to the study procedures specified in this protocol up to the scheduled date of study completion, or up to recovery or stabilization of any AE to be followed-up as specified in this protocol, whichever comes last.

If possible, and after the permanent discontinuation of treatment, the patients will be assessed using the procedures normally planned for the last dosing day with the IMP (this EOT visit should take place within 5 days of treatment discontinuation, if possible) including a PK sample, if appropriate.

The patient, at a minimum, should then be followed-up for 4 weeks from the last administration of IMP or until recovery or stabilization of any AE as specified in this protocol, whichever comes last. A final end of study visit will take place 4 weeks after the premature discontinuation.

All cases of permanent treatment discontinuation should be recorded by the Investigator in the appropriate pages of the e-CRF when considered as confirmed. IRT should be notified when a patient prematurely discontinues study treatment. In the medical record, at least the date of the withdrawal and the reason should be documented.

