11.4.4 Analyses of safety data

Safety data will be presented on the safety population of the parallel-arm period and of the single-arm period. Treatment-emergent adverse events (TEAEs), treatment-emergent SAEs, treatment-emergent AESIs, and TEAEs leading to treatment discontinuation, will be summarized based on the Medical Dictionary for Regulatory Activities (MedDRA) coding of verbatim terms reported by investigators (Section 9.2.5).

All safety analyses will be performed using the following common rules:

- The observation period to be used for the safety population is the TEAE period. The TEAE period is defined
 - For the parallel-arms period as the time from the first IMP injection to the day before the second IMP injection (for patients entering into the single arm period period) or to 70 days after the first IMP injection, whichever comes first
 - For the single-arm period as the time from the first IMP injection received in the single arm period to 70 days after the last IMP injection.

The following definitions will be applied to laboratory parameters, and vital signs:

- The potentially clinically significant abnormality (PCSA) values are defined as abnormal values considered medically important by the Sponsor according to predefined criteria/thresholds based on literature review and defined by the Sponsor for clinical laboratory tests, and vital signs.
- Potentially clinically significant abnormality criteria will determine which patients had at least 1 PCSA during the TEAE period, taking into account all evaluations performed, including unscheduled or repeated evaluations. The number of all such patients will be the numerator for the on-treatment PCSA percentage.

- Treatment period: the treatment period used for quantitative analysis is defined:
 - For the parallel-arms period as the time from the first IMP injection to 35 days after this injection or to the day before the second IMP injection (for patients entering into the single arm period period) whichever comes first.
 - For the single-arm period as the time from the first IMP injection received in the single arm period to 35 days after the last IMP injection.

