2.1.4.5 Safety endpoints

The safety analysis will be based on the reported adverse events including SAE AESIs and other safety information, such as clinical laboratory data and vital signs.

Observation period

The period of safety observation starts from the time when the patient gives informed consent and is divided into the following periods:

- The pre-treatment period: defined as the time from the signed informed consent up to the first IMP injection;

- The TEAE period of the parallel-arm period defined as the time from the first IMP injection to the day before the second IMP injection for patients entering into the single arm period or to 70 days after the first IMP injection, whichever comes first;
 - The TEAE period of the parallel-arm period will include the TREATMENT period defined as the time from the first IMP injection to the day before the second IMP injection for patients entering into the single arm period, or to 35 days after the first IMP injection, whichever comes first.
- The TEAE period of the single-arm period is defined as the time from the second IMP injection up to the day of last IMP injection + 70 days.
 - The TEAE period of the single-arm period will include the TREATMENT period defined as the time from the second IMP injection up to the day of last IMP injection + 35 days.
- The post-treatment period: defined as the time starting 71 days after the day of last IMP injection.

The on-study observation period of the parallel-arm period is defined as the time from the day of first IMP injection until the Week 4 visit of the patient, if done, or 4 weeks after the randomization of the patient.

The on-study observation period of the single-arm period is defined as the time from the second IMP injection until the Week 16 visit of the patient, if done, or 16 weeks after the randomization of the patient.

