- Neurologic events selected using a CMQ, based on SMQs “demyelination” (broad and narrow), “peripheral neuropathy” (broad and narrow), and “Guillain-Barre syndrome” (broad and narrow) excluding the following PTs “acute respiratory distress syndrome”, “asthenia”, “respiratory arrest” and “respiratory failure” and including selected PTs from SMQ "optic nerve disorders" (see [Table 2](#) for the list of terms)
- Neurocognitive events:
 - Selected using a CMQ, based on the following 5 HLGTS: “deliria (including confusion)”, “cognitive and attention disorders and disturbances”, “dementia and amnesic conditions”, “disturbances in thinking and perception”, and “mental impairment disorders”
 - A second grouping of terms for neurocognitive events was defined based on Regulatory Agency request (see [Table 3](#) for the list of terms)
- Pregnancy occurring in a female patient (including male subject’s partner) selected using appropriate MedDRA codes.
- Symptomatic overdose with IMP, selected using events reported as “Overdose of Alirocumab” and with “symptomatic overdose ticked “Yes” in the “Overdose” e-CRF page;

2.1.4.5.2 *Deaths*

The deaths observation period are per the observation periods defined above.

- Death on-study during the parallel-arm period: deaths occurring during the on-study observation period of the parallel-arm period,
- Death on-treatment during the parallel-arm period: deaths occurring during the TEAE period of the parallel-arm period,
- Death on-study during the single-arm period: deaths occurring during the on-study observation period of the single-arm period,
- Death on-treatment during single-arm period: deaths occurring during the TEAE period of the single-arm period,
- Death post-study: deaths occurring after the on-study period.

2.1.4.5.3 *Laboratory safety variables*

Clinical laboratory data consist of blood analysis, including hematology and clinical chemistry, and urinalysis. Clinical laboratory values will be analyzed into international units. International units will be used in all listings and tables. Clinical laboratory values converted into conventional (US) units will be also available in the database. Analyses can be provided upon request.

The laboratory parameters (excluding those considered as pharmacodynamic parameters) will be classified as follows:

- Hematology
 - Red blood cells count and platelets: hemoglobin, hematocrit, platelet count, Red blood cells count

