- Number (%) of patients who died by study period (on-study, on-treatment, post-study) Deaths in nonrandomized patients or randomized but not treated patients.

- TEAEs leading to death (death as an outcome on the AE reported by the Investigator) by primary SOC , HLGT, HLT, and PT showing number (%) of patients sorted by internationally agreed SOC order, with HLGT, HLT, and PT presented in alphabetical order within each SOC .
- TEAEs leading to death (death as an outcome on the AE as reported by the Investigator) by primary SOC, HLGT, HLT, and PT. TEAEs leading to death are TEAEs that led to death regardless of timing of death in relation to IMP injection (i.e. death occurring in the TEAE period or during the post-treatment period).

2.4.4.2.5.3 Laboratory variables

The summary statistics (including number, mean, median, standard deviation, minimum and maximum) of all laboratory variables (central laboratory values and changes from baseline) will be calculated for each visit or study assessment (baseline, each post-baseline time point, last on-treatment and worst on-treatment value).

The incidence of PCSAs (list provided in [Appendix A](#)) at any time during the TEAE period will be summarized by biological function irrespective of the baseline level and/or according to the following baseline status categories:

- Normal/missing
- Abnormal according to PCSA criterion or criteria

For parameters for which no PCSA criteria are defined, similar table(s) using the normal range will be provided.

Drug-induced liver injury

The liver function tests, namely AST, ALT, ALP, and total bilirubin, are used to assess possible drug-induced liver toxicity. The proportion of patients with PCSA values or ALT increase as defined in Adverse Events of Special Interests section (see [Section 2.1.4.5.1](#)) during TEAE period by baseline status will be displayed for each parameter.

An evaluation of drug-induced serious hepatotoxicity with the graph of distribution of peak values of ALT versus peak values of total bilirubin will also be presented using post-baseline values during TEAE period. Note that the ALT and total bilirubin values will be presented on a logarithmic scale. The graph will be divided into 4 quadrants with a vertical line corresponding to 3 x ULN for ALT and a horizontal line corresponding to 2 x ULN for total bilirubin.

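### A treated patient who never takes injection 2 has no on-study time after about Day 29 under the SAP, so a death in later protocol follow-up would be tabulated as post-study (minor)

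*SAP*

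**What the plan says.** SAP 2.1.4.5 sets two kinds of period for each phase.

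- **Treatment-emergent (TEAE), parallel-arm phase:** from the first injection to the day before injection 2 "for patients entering into the single arm period or to 70 days after the first IMP injection, whichever comes first". Protocol 11.4.4 has the same limit: "to 70 days after the first IMP injection, whichever comes first".
- **On-study, parallel-arm phase:** from the first injection "until the Week 4 visit of the patient, if done, or 4 weeks after the randomization of the patient".
- **On-study, single-arm phase:** from injection 2 to the Week 16 visit if done, or 16 weeks after randomization.

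The Deaths subsection (SAP 2.1.4.5.2) calls a death on-treatment if it falls in a TEAE period, and adds: "Death post-study: deaths occurring after the on-study period". SAP 2.4.4.2.5.2 then tabulates "Number (%) of patients who died by study period (on-study, on-treatment, post-study".

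On follow-up after permanent discontinuation, Protocol 10.3.4 states: "Patients will be followed-up according to the study procedures specified in this protocol up to the scheduled date of study completion", or until adverse events settle if that is later. The same section also places a final visit 4 weeks after premature discontinuation and sets a minimum follow-up of 4 weeks from the last dose.

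On the purpose of the randomized phase, Protocol 4.2.2 says: "It also allows for a descriptive comparison of the two devices up to Week 4 only (after the first dose".

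**The concern.** The single-arm on-study period depends on receiving injection 2. For a treated patient who never receives it, that period does not exist, and the parallel-arm period has already closed at about Week 4. The protocol nevertheless keeps such a patient under observation, and Protocol 10.3 asks that patients remain in the study as long as possible after stopping treatment. A death in that follow-up would appear in the study report as having occurred after the study.

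The same dependence on injection 2 gives the by-device parallel-arm safety tables unequal windows. Percentages of patients with a TEAE use the safety population as denominator (Protocol 11.4.4.1), with no adjustment for observation time. Whether a patient gets the longer window is settled after randomization and may be related to tolerability.

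**Working it through.** **Calendar.** Take randomization and first injection both on Day 1.

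- Week 4 visit: Day 29 ± 3, so Days 26 to 32. Four weeks after randomization: 1 + 28 = Day 29.
- Sixteen weeks after randomization: 1 + 112 = Day 113.
- TEAE end without injection 2: 1 + 70 = Day 71.

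**Two patients side by side.**

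| | Stops after injection 1 | Stops after injection 2 (Day 29) |
|---|---|---|
| Parallel-arm on-study | Day 1 to about Day 29 | Day 1 to about Day 29 |
| Single-arm on-study | does not exist | Day 29 to Day 113 |
| Protocol follow-up rules | Section 10.3.4 | Section 10.3.4 |

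The follow-up rules are the same for both, but the on-study label is not.

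**Length of the gap for the first patient, under each sentence of Protocol 10.3.4.**

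- Follow-up to scheduled completion: Days 30 to 113, or 113 − 29 = 84 days. In Days 30 to 71 (71 − 29 = 42 days) a death is both on-treatment and post-study. In Days 72 to 113 (113 − 71 = 42 days) it is post-study only.
- Final visit 4 weeks after discontinuation, stopping at Day 29: 29 + 28 = Day 57. The gap is Days 30 to 57, or 57 − 29 = 28 days, all within the TEAE period.
- Minimum of 4 weeks from the last dose: 1 + 28 = Day 29. There is no gap.

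**By-device windows.** With injection 2 on Day 26, 29 or 32, the parallel-arm TEAE period ends on Day 25, 28 or 31. Without injection 2 it runs a nominal 70 days, and 70/28 = 2.5.

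The documents give neither a TEAE rate nor the number of patients lost before injection 2. As an illustration, assume a 28-day risk *r* with constant hazard, and *k* of 33 patients in an arm without injection 2, all observed for the full 70 days:

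- 70-day risk: r70 = 1 − (1 − r)^2.5
- Arm percentage: ((33 − k) × r + k × r70) / 33

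| Assumed r | r70 | k = 1 | k = 3 |
|---|---|---|---|
| 10% | 23.2% | 10.4% | 11.2% |
| 20% | 42.8% | 20.7% | 22.1% |
| 30% | 59.0% | 30.9% | 32.6% |
| 40% | 72.1% | 41.0% | 42.9% |

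Each such patient adds about 0.4 to 1.0 percentage point to the arm. One patient in 33 is 3.0 points. The k = 3 column places roughly the whole planned 10% drop-out of one arm (0.10 × 33 = 3.3) before injection 2.

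**The case against.** **Deaths.** No death disappears: SAP 2.4.4.2.5.2 tabulates TEAEs leading to death whatever the timing of the death. That stands, and it confines the matter to labelling.

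A reader might infer that a death on Days 30 to 71 carries two contradictory labels. The documents do not support that. SAP 2.1.4.5.2 defines on-study by calendar and on-treatment by exposure, and nowhere makes them exclusive. Nor do completers share the defect on Days 114 to 155 (85 + 70 = 155): a death after the final visit but within 70 days of the last dose is properly both.

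A reader might also take 84 days as the established gap. It depends on one of the sentences in Protocol 10.3.4 that have yet to be reconciled.

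**By-device windows.** It is tempting to call the 70-day limb an error that biases the device comparison and should be replaced by the 35-day treatment limit. Several points tell against this:

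- The limb is an explicit provision for patients without injection 2, and the protocol shares it.
- A 35-day cut would still leave 35 days against 28, and would drop later events from the main table.
- Adverse events are recorded only to the end of study, so the observed window may be well short of 70 days.
- A patient who stopped because of a reaction is already counted, and a longer window cannot raise that patient's contribution to the any-TEAE percentage.
- The comparison is descriptive, discontinuations are tabulated by arm (SAP 2.2), and injection-site reactions are also reported per injection and by time to first reaction.

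These points justify keeping the 70-day tables. They do not answer the difference in on-study time between a patient who stops after injection 1 and one who stops after injection 2.

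**Conclusion.** The on-study definition has a gap for treated patients who never take injection 2. Read literally, an in-follow-up death in such a patient is labelled post-study, while the same death in a patient who stopped after injection 2 is labelled on-study. The gap is 84 days if follow-up runs to Day 113, and 28 days if a final visit follows a Day 29 stop by 4 weeks. It vanishes only under the 4-week minimum from the last dose.

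The unequal by-device TEAE and abnormality (PCSA) windows are real but secondary. They are about 28 days for patients who take injection 2 on schedule and nominally 70 for those who never do; a patient who misses Week 4 and resumes at Week 8 has about 56. The effect is at most about 1 point per non-continuer under the assumed risks. It distorts the device contrast only if early stopping differs between arms.

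Both matters are minor. Few deaths and few early non-continuers are expected in 66 patients, and the primary device endpoint is untouched.

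**What to change.** **On-study (SAP 2.1.4.5 and 2.1.4.5.2).** Define on-study for every treated patient as first IMP injection to the Week 16 visit if done, or 16 weeks after randomization, whether or not injection 2 is given. Define post-study as after that date. State that on-treatment is a separate flag that may overlap with either. This extends to all treated patients the end date the SAP already uses for those who take injection 2. Protocol 11.4.4.1 asks for deaths by on-study period without giving dates for it, so no conflict arises. The cost is a few lines of wording.

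**Protocol 10.3.4.** Reconcile the statements on how long patients are followed after permanent discontinuation. Which one governs is for the sponsor to settle.

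**By-device safety tables.** Keep the 70-day tables, so the window shared with Protocol 11.4.4 is unchanged. Add a supplementary by-device table cut for all patients at the earlier of the day before injection 2 and Day 28, to match the stated Week 4 comparison. List later events in non-continuers separately. The cost is one table and one listing.

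One caution on the PCSA version: the flow chart schedules no safety laboratory tests or vital signs between Day 1 and the Week 4 visit. The SAP should therefore say whether Week 4 visit measurements taken before injection 2 count, or the supplementary PCSA table will be nearly empty.

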2.1.4.5.1 Adverse events variables

Adverse events (including SAEs and AESIs) are recorded from the time of signed informed consent until the end of study.

All AEs will be coded to a “lowest level term”, “PT”, “HLT”, “HLGT”, and associated primary “SOC” using the version of MedDRA currently in effect at Sanofi at the time of database lock.

Adverse event observation period

- Pre-treatment AEs are AEs that developed or worsened or became serious during the pretreatment period.
- Treatment-emergent adverse events are AEs that developed or worsened or became serious during the TEAE period.
- Post-treatment AEs are AEs that developed or worsened or became serious during the post-treatment period.

Adverse events of special interest

AESIs are AEs (serious or non-serious) that need to be monitored, documented, and managed in a pre-specified manner described in the protocol. In this study, AESI are the following (their complete descriptions are provided in the protocol):

- Local injection site reactions, selected using e-CRF specific tick box on the AE page;
- Allergic events:
 - General allergic events will be tabulated. Events will be selected using standardized MedDRA query (SMQ) “hypersensitivity” (broad and narrow) excluding the following PTs linked to local injection site reactions (“infusion site dermatitis”, “infusion site hypersensitivity”, “infusion site rash”, “infusion site urticaria”, “injection site dermatitis”, “injection site hypersensitivity”, “injection site rash”, “injection site urticaria” and “injection site vasculitis”);
 - General allergic events and local allergic reactions at IMP injection site will be described. This selection will be based on the above selection for general allergic event and on the following selection of PT from the symptoms complementary form for local injection site reaction ("Injection site dermatitis", "Injection site hypersensitivity", "Injection site oedema", "Injection site rash", "Injection site urticaria", "Injection site eczema", "Injection site vasculitis", "Injection site swelling", "Infusion site dermatitis", "Infusion site hypersensitivity", "Infusion site oedema", "Infusion site rash", "Infusion site urticaria", "Infusion site swelling")
- ALT ≥ 3 ULN (if baseline ALT < ULN) or ALT ≥ 2 times the baseline value (if baseline ALT \geq ULN), selected using laboratory data
- Neurologic events selected using a CMQ, based on SMQs “demyelination” (broad and narrow), “peripheral neuropathy” (broad and narrow), and “Guillain-Barre syndrome” (broad and narrow) excluding the following PTs “acute respiratory distress syndrome”, “asthenia”, “respiratory arrest” and “respiratory failure” and including selected PTs from SMQ "optic nerve disorders" (see [Table 2](#) for the list of terms)
- Neurocognitive events:
 - Selected using a CMQ, based on the following 5 HLGTS: “deliria (including confusion)”, “cognitive and attention disorders and disturbances”, “dementia and amnesic conditions”, “disturbances in thinking and perception”, and “mental impairment disorders”
 - A second grouping of terms for neurocognitive events was defined based on Regulatory Agency request (see [Table 3](#) for the list of terms)
- Pregnancy occurring in a female patient (including male subject’s partner) selected using appropriate MedDRA codes.
- Symptomatic overdose with IMP, selected using events reported as “Overdose of Alirocumab” and with “symptomatic overdose ticked “Yes” in the “Overdose” e-CRF page;

2.1.4.5.2 *Deaths*

The deaths observation period are per the observation periods defined above.

- Death on-study during the parallel-arm period: deaths occurring during the on-study observation period of the parallel-arm period,
- Death on-treatment during the parallel-arm period: deaths occurring during the TEAE period of the parallel-arm period,
- Death on-study during the single-arm period: deaths occurring during the on-study observation period of the single-arm period,
- Death on-treatment during single-arm period: deaths occurring during the TEAE period of the single-arm period,
- Death post-study: deaths occurring after the on-study period.

2.1.4.5.3 *Laboratory safety variables*

Clinical laboratory data consist of blood analysis, including hematology and clinical chemistry, and urinalysis. Clinical laboratory values will be analyzed into international units. International units will be used in all listings and tables. Clinical laboratory values converted into conventional (US) units will be also available in the database. Analyses can be provided upon request.

The laboratory parameters (excluding those considered as pharmacodynamic parameters) will be classified as follows:

- Hematology
 - Red blood cells count and platelets: hemoglobin, hematocrit, platelet count, Red blood cells count
 - White blood cells: White blood cells count, White blood cells differential (neutrophils, lymphocytes, monocytes, basophils, eosinophils)
- Clinical chemistry
 - Metabolism: glucose, total protein, albumin, creatine phosphokinase
 - Electrolytes: sodium, potassium, chloride, calcium.
 - Renal function: estimated glomerular filtration rate, creatinine, urea nitrogen
 - Liver function: ALT/ Serum Glutamic-Pyruvic Transaminase, AST/ Serum Glutamooxaloacetate Transferase, ALP, albumin, total bilirubin, Gamma-Glutamyl Transferase.

2.1.4.5.4 *Vital signs*

Vital signs parameters include heart rate, systolic and diastolic blood pressure measured after 5 minutes in seating resting position.

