9.2 SECONDARY ENDPOINTS

- Secondary endpoints include: Device-related endpoints
- Pharmacokinetics
- Anti-drug antibodies
- Efficacy/pharmacodynamics:
- Safety:
 - Adverse events (AEs), including Serious Adverse Events (SAEs) and Adverse events of special interest (AESIs), laboratory data, and vital signs assessed throughout the study.

AESIs and other groupings of interest will include: general allergic reactions (GARs) requiring consultation with another physician, LISR requiring consultation with another physician, neurologic events that require additional examinations/procedures and/or referral to a specialist, neurocognitive events, pregnancy, symptomatic overdose with IMP, alanine aminotransferase (ALT) increase: $ALT \geq 3 \times$ Upper Limit of Normal (ULN) (if baseline $ALT < ULN$) or $ALT \geq 2$ times the baseline value (if baseline $ALT \geq ULN$).

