 - Any general allergic events regardless of the cause that require consultation with another physician for further evaluation of hypersensitivity/allergy as per the Investigator's medical judgment should be reported as an AESI.
 - All general allergic events require completion of the specific e-CRF screen.

- **Local injection site reactions:**

- Local injection site reactions that require consultation with another physician for further evaluation of hypersensitivity/allergy as per the Investigator's medical judgment should be reported as an AESI.

All LISR require completion of the specific e-CRF screen.

Note:

- Other LISR are non-AESIs. Please see [Section 10.6](#) for details.
 - The safety instructions on allergic events and LISR are detailed in [Section 10.6](#).
- **Neurologic events:** neurologic events that require additional examinations/procedures and/or referral to a specialist should be reported as an AESI. If the event does not require additional examinations/procedures and/or referral to a specialist, it should be reported as a standard AE.
 - **Neurocognitive events:** All neurocognitive events will be considered as AESI.

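### For injection site, allergic and neurologic events, the SAP labels as AESI a set chosen without the protocol's AESI criterion

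*SAP*

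**What the plan says.** **Protocol.** Section 10.4.1.3 defines the AESIs and ties three categories to what the event required:

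- LISR: "Local injection site reactions that require consultation with another physician for further evaluation of hypersensitivity/allergy", with the explicit note "Other LISR are non-AESIs". Section 9.2 repeats the condition ("LISR requiring consultation with another physician"), as does Table 9.
- General allergic events: "Any general allergic events regardless of the cause that require consultation with another physician for further evaluation of hypersensitivity/allergy".
- Neurologic events: "neurologic events that require additional examinations/procedures and/or referral to a specialist should be reported as an AESI". Without such a need, the event is an ordinary AE.

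**SAP.** Section 2.1.4.5.1 introduces its list with "In this study, AESI are the following (their complete descriptions are provided in the protocol", and then gives a selection rule for each category:

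- LISR: "Local injection site reactions, selected using e-CRF specific tick box on the AE page".
- General allergic events: the hypersensitivity SMQ (standardized MedDRA query), broad and narrow, less a list of injection-site and infusion-site terms.
- Neurologic events: "Neurologic events selected using a CMQ, based on SMQs" for demyelination, peripheral neuropathy and Guillain-Barre syndrome, less four terms and plus selected optic nerve terms. A CMQ is a company MedDRA query.

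SAP 2.4.4.2.5.1 builds the AESI tables from these selections. It plans no table of events that the investigator reported as AESIs.

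**The concern.** AESIs are named in the protocol's secondary safety endpoint, and the synopsis has them tabulated by device. A reader of the study report will take a table headed AESI to mean the events that met the protocol's definition, which sites had to notify within 24 hours. In three categories the SAP's rules answer a different question: whether the event was flagged or coded in a certain way, and not whether it led to a consultation, a work-up or a referral. An ordinary reaction may then carry a label that the protocol denies it, and an event that a site did report as an AESI may be absent from the tables with that name.

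**Working it through.** No arithmetic applies: the point depends on no rate, power or sample size. The check sets protocol 10.4.1.3 beside SAP 2.1.4.5.1, category by category.

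| Category | Protocol condition | SAP selection | Result |
|---|---|---|---|
| LISR | Another physician consulted about hypersensitivity or allergy; all others excluded | AE-page tick box, no consultation condition | SAP wider |
| General allergic | Same consultation condition, whatever the cause | Hypersensitivity SMQ less listed terms, no consultation condition | SAP wider; an event coded outside the SMQ is not picked up |
| Neurologic | Extra work-up or referral, no restriction by term | CMQ on named topics, no work-up or referral condition | SAP wider inside the CMQ, narrower outside it |
| Symptomatic overdose | IMP or NIMP in 10.4.1.3; IMP only in 9.2 | Alirocumab only | Protocol inconsistent; SAP matches 9.2 |
| ALT increase | Two thresholds by baseline ALT | Same thresholds, from laboratory data | Agree |
| Pregnancy | Patient, or partner of a male patient | Same, by MedDRA code | Agree |
| Neurocognitive | All events | Two term groupings, no further condition | Agree in substance; only coding coverage can differ |

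Two consequences follow.

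1. **Too wide.** Take a patient with an injection site reaction recorded as an AE, ticked as LISR, with no consultation. Under the protocol this is not an AESI. Under the SAP it is in the LISR set listed as AESI. The same reasoning holds for an event in the hypersensitivity SMQ without consultation, and for an event in the neurologic CMQ without work-up or referral.

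2. **Too narrow.** Take a neurologic event that is referred to a specialist, and so reported as an AESI, but coded to a term outside the CMQ. No SAP selection picks it up as a neurologic AESI. It still appears in the TEAE tables by system organ class and preferred term and, if serious, in the serious TEAE tables.

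One step is an inference. The e-CRF page is not in the documents, so they do not state that the tick box marks every LISR. The text points that way: protocol 10.4.1.3 requires the specific screen for all LISR, and SAP 2.4.4.2.5.1 tabulates LISR by intensity from mild upwards and per injection received. The box can mark only reactions recorded as AEs. Protocol 10.6.1 generally exempts isolated redness or swelling under 2.5 cm from AE reporting, so those would not be counted.

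**The case against.** The case for leaving the plan alone has real force.

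- **Groupings are foreseen.** Protocol 11.4.4.1 says that AESIs in the tables may be defined by preferred term or prespecified grouping. This stands: using queries is not the defect, and the statement in SAP 1.5 that nothing was modified is defensible. But permission to use a grouping does not make a given grouping select the protocol's AESIs.
- **All LISR are wanted.** The synopsis names LISR among the tabulated AESIs without the condition. Protocol 4.2.2 and 9.5 put LISR, unqualified, in the Week 4 device comparison, and 9.2 speaks of AESIs together with other groupings of interest. This stands too: the full LISR table is needed and should stay. It does not make every reaction an AESI against the explicit exclusion in 10.4.1.3.
- **The SAP defers to the protocol.** Its introductory sentence refers there for the full descriptions, and the heading of the analysis part already speaks of groupings that include selected AESIs. That softens the conflict, but the rules a programmer would follow do not apply the condition.

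A reader might go further and infer that each ordinary reaction raises an arm's AESI rate by a calculable amount. The documents do not support that. The TEAE overview has four rows (any, serious, leading to death, leading to permanent discontinuation) and no AESI row. Each grouping is tabulated separately, so patients with an LISR appear as patients with an LISR.

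A reader might also infer that safety information is lost, or that the whole AESI list departs from the protocol. Neither holds: missed events stay in the general TEAE tables, and ALT, pregnancy and neurocognitive events agree in substance.

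**Conclusion.** The point holds for LISR, general allergic events and neurologic events. The SAP calls AESI a set chosen without the protocol's consultation, work-up or referral condition, and its neurologic query can omit an event that was reported as an AESI. Separately, the protocol contradicts itself on whether symptomatic overdose covers background drugs, and those places must be reconciled with the SAP.

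The severity is minor. The effect is confined to the labelling and content of descriptive secondary safety tables. No inferential safety test is planned, and the primary endpoint and sample size are untouched. No numerical size can be given, because the SAP plans no pooled AESI rate and the documents give no expected frequency of these events. The LISR part rests on the inference that the tick box marks all LISR recorded as AEs. If it marks only those that led to a consultation, that part falls away and the allergic and neurologic parts remain.

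**What to change.** 1. Add one table or listing per study period of TEAEs that the investigator reported as AESIs under protocol 10.4.1.3, by device in the parallel-arm period and overall in the single-arm period.
2. Keep the tick-box, SMQ and CMQ tables as planned, but title them *groupings of interest*.
3. Amend the SAP 2.1.4.5.1 sentence that introduces the list, so that it describes groupings for analysis and leaves the AESI definition to the protocol.
4. Reconcile the overdose wording between protocol 9.2, protocol 10.4.1.3 and SAP 2.1.4.5.1.

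The cost is one extra output per period and a few lines of text. The protocol already requires AESI notification through e-CRF screens and additional AESI forms (9.2.5, 10.4.1.3, Table 9), so no new data collection should be needed, provided that the AESI report can be identified in the database. No planned output is lost.
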